Generally, only data of pre-specified planned visits will be used in statistical summary analyses, and calculations of any derived parameters; data of unscheduled visits will be included in the listings only.

Actual, rather than planned, sampling time points will be used in the derivation of PK parameters and in the individual concentration-time plots and listing of PK concentration data. Planned sampling time points will be used in the descriptive summaries and in mean and median plots. Concentration-time data will be listed according to actual sampling time points relative to dosing time.

Assessment windows will not be defined for classifying measurements obtained outside scheduled assessment times.

7.1 **Coronavirus Disease 2019 (COVID-19) Impact**

As it is expected that the COVID-19 pandemic will be ongoing during the conduct of the study, the impact of COVID-19 will be assessed and reported.

Primary Estimand

The primary estimand is defined in [Section 10.1.1](#) and is taking into account intercurrent events such as:

- missed doses which might be caused by issues in the drug delivery to the patient due to COVID-19, the COVID-19 disease itself or COVID-19 vaccination scheduling/side effects (intercurrent event of non-compliance to treatment);
- early treatment or study discontinuation which might be caused by COVID-19 (intercurrent events of early treatment or study discontinuation).

Further events introduced by COVID-19 (for example concomitant medications used to treat COVID-19 or vaccinations) will be assessed in the Blind Data Review Meeting (BDRM) and might lead to an exclusion of a subject or subject's data from the PP Analysis Set which is the study analysis set defined for the supplementary analysis of the primary estimand. HAE attacks

will be also assessed during BDRM if those could be triggered by COVID-19 and decision will be made to exclude those subjects or subject's data from the PP Analysis Set.

Subject Disposition: Study Treatment Discontinuation or Study Discontinuation

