8.3 Study Periods relative to Treatment

The following definitions for the periods of efficacy and safety will be used to define the durations used in the denominator of the time-normalized endpoints and safety endpoints such as exposure and subject-years.

Table 8 Overview Study Periods

Study Period	Start Date	End Date	Duration
Screening Period	date of Informed Consent	date/day on which eligibility for Run-in Period was confirmed	Day 1 Visit date of Run-in Period – date of Informed Consent
Run-in Period	date/day on which eligibility for Run-in Period was confirmed	date of the Day 1 Visit of Treatment Period	Day 1 Visit date of the Treatment Period or Date of Run-in Completion/Non-completion [whichever is first] – Day 1 Visit date of Run-in Period

Study Period	Start Date	End Date	Duration
Treatment Period/ Efficacy Evaluation Period	date of the Day 1 Visit of Treatment Period	date of the Day 182 Visit of the Treatment Period or the End of Study date for subjects who prematurely discontinued [whichever occurs earlier]	Day 182 Visit date of the Treatment Period or End of Study date [whichever is first] – Day 1 Visit date of the Treatment Period + 1
Follow-up Period	date of the Day 182 Visit of the Treatment Period	date of the Follow-up/Final Visit (Day 242 Visit)	date of the Follow-up/Final Visit (Day 242 Visit) – date of the Day 182 Visit of Treatment Period
Safety Period	date and time of the first administration of investigational product	Date of End of Study	Date of End of Study - date of the first administration of investigational product

Technical Notes:

- Screening Period: The first day of the Run-in Period may occur on the same day as the Screening Visit for subjects meeting the eligibility criteria for the Run-in Period. Those subjects will then have no Screening Period.
- Run-in Period: The eCRF ‘Study Completion’ form will only be completed for subjects in the Treatment Period. Thus, if a subject is not eligible for treatment the Run-in Non-Completion is captured on the ‘Treatment Period Inclusion Criteria’ form.
- Follow-up Period: A Follow-up Period will be only available for subjects who did not roll over to CSL312_3002.

9 Study Population

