10.1 Analysis of Primary Endpoint

The primary endpoint is the time-normalized number of HAE attacks per month during the Treatment Period from Day 1 (first study drug administration) through Day 182 (inclusive).

Subjects will enter HAE symptoms into their eDiary, the start and end date and time, the interference of HAE symptom(s) with daily activities, and location(s) of the HAE symptom(s). Investigator-reported HAE attacks will be based upon review of subject diaries, relevant interval medical history, and physician judgment. The investigator may ask clarifying questions to assist in his/her assessment of whether or not an HAE attack occurred. If an attack occurred, then the investigator will record an attack in the eCRF form, the start/end date and time, the attack location(s), and the severity of the attack based on the most severe symptoms. For every visit, the investigator will report all HAE attacks that have occurred in the interim since the last visit the subject attended.

For all analyses considering HAE attacks, only the HAE attacks confirmed and reported by the investigator using the eCRF ‘HAE Attacks’ form will be used.

HAE attacks with a start date on or after the first day of the Run-in Period but prior to the date and time of the first study drug administration will be counted for the Run-in Period.

HAE attacks with a start date and time after the first study drug administration through Visit Day 182 (inclusive) or End of Study visit (whatever is first) will be counted for the Treatment Period and will be included in the analyses of efficacy.

The primary endpoint will be analyzed using the ITT and PP Analysis Set. The ITT Analysis Set will be used as the primary analysis and the PP Analysis Set will be used as the supplementary analysis (see [Section 10.1.3](#)).

The primary endpoint, time-normalized number of HAE attacks per month, is calculated per subject as:

$$[\text{the number of HAE attacks} / \text{length of subject treatment in days}] * 30.4375$$

where the length of subject treatment is calculated as:

$$[\text{the date of Study Visit Day 182 or the End of Study date [whatever is first]} - \text{the date of Study Visit Day 1 of the Treatment Period} + 1].$$

To transform the length of subject treatment which are calculated in days in years the number of days is divided by 365.25. Thus, time-normalized number of HAE attacks per year is calculated per subject as:

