10.1.1 Primary Estimand

The primary interest is to assess the treatment effect of CSL312 during treatment from Day 1 through Day 182 while subjects are allowed to treat HAE attacks with on-demand medications.

The primary estimand in line with the primary interest of the study follows the treatment policy strategy and is described as follows:

- Treatment Condition: monthly treatment of CSL312 or placebo
- Population: the target patient population defined by eligibility criteria and who were randomized (ITT).
- Variable: time-normalized number of HAE attacks per month during treatment from Day 1 through Day 182.

Intercurrent events: The occurrence of an intercurrent event is irrelevant. All observed values will be used regardless of occurrence of any of the following intercurrent events:

- administration of on-demand medication in addition to prophylactic treatment with CSL312,
- Prohibited concomitant medications due or not due to COVID-19 or COVID-19 vaccination,
- non-compliance to treatment due or not due to COVID-19 or COVID-19 vaccination,
- early study discontinuation due or not due to COVID-19.

- Population-level summary: median time-normalized number of HAE attacks per month during treatment from Day 1 through Day 182 by treatment.

If a subject discontinued the study early after being continuously the first 30 days in the treatment period, the observation is terminated by the Early Termination Visit. It is assumed that the attack rate for subjects, who discontinued the study after the 30th study day and before the end of the 6th month, is comparable to the attack rate from subjects who have the entire 6 months treatment period observed. This assumption is based on CSL312_2001 data which showed that the CSL312 treatment effect was maintained over time. Therefore, the primary endpoint will be considered measurable and not missing, ie, the time-normalized number of HAE attacks will be calculated based on the HAE attacks reported until the Early Termination Visit.

In case a subject discontinues study treatment due or not due to COVID-19 but continues participation in the study for more than 30 days beyond the last study drug administration,

the HAE attacks until the last study drug administration plus 30 days will be included in the HAE attack analysis and length of subject treatment in days will be derived as:

[date of last study drug administration – the date of Study Visit Day 1 of the Treatment Period +31].

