10.1.3 Supplementary Analyses of Primary Estimand

The primary estimand described above is complemented by an additional supplementary estimand and analysis.

Only subjects in the PP Analysis Set will be included. The interest is to assess the treatment effect of CSL312 during treatment from Day 1 through Day 182 while subjects are allowed to treat HAE attacks with on-demand medications but excluding subjects who do not comply with the protocol.

The additional estimand in line with the interest of the study follows the treatment policy strategy and is described as follows:

- Treatment Condition: monthly treatment of CSL312 or placebo.
- Population: the target subject population defined by eligibility criteria, who were randomized, received at least 1 dose of CSL312 and who comply with the protocol (PP).
- Variable: time-normalized number of HAE attacks per month during treatment from Day 1 through Day 182.
- Intercurrent events: The occurrence of an intercurrent event is irrelevant. All observed values will be used regardless of occurrence of any of the following intercurrent events:

- administration of on-demand medication in addition to prophylactic treatment with CSL312,
- early study discontinuation due or not due to COVID-19.
- Population-level summary: descriptive statistics of the time-normalized number of HAE attacks during treatment from Day 1 through Day 182 by treatment.

When a subject who was at least 30 days in the treatment period after the first study drug administration discontinues study treatment due or not due to COVID-19 but stays beyond the last study drug administration in the study for more than 30 days, the HAE attacks until the last study drug administration plus 30 days thereafter will be included in the supplementary analysis of the primary estimand.

If a subject has a COVID-19 infection while participating in the study, his/her attacks will be assessed during the BDRM to determine if they might be caused/triggered by other factors, e.g. COVID-19. If there is clear evidence that they are due to the COVID-19 infection or other, they might be excluded from the analyses. Missed study drug administrations not due or due to COVID-19 or COVID-19 vaccination might also lead to the exclusion of a subject or subject's data from the supplementary analysis as well as prohibited concomitant medications due or not due to COVID-19 or COVID-19 vaccination.

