10.3.2.3 The time-normalized number of moderate or severe HAE attacks

For the analysis of the time-normalized number of moderate or severe HAE attacks, an analogue calculation and analyses as described in [Section 10.3.2.2](#) will be done considering all HAE attacks classified as moderate or severe.

10.3.2.4 Time-normalized number of HAE attacks at various time points during the Treatment Period

The time-normalized number of HAE attacks (per month and annualized) during, the first 3-months Treatment Period and the second 3-months Treatment Period will be summarized descriptively and compared between the treatment arms using a two-sided Wilcoxon Test with alpha = 5%.

The time-normalized number of HAE attacks (per month) for the different Treatment Periods is calculated for a subject as:

[number of HAE attacks within first 3-months or second 3-months Treatment Period/ length of subject treatment in days] * 30.4375

and the time-normalized number of HAE attacks (annualized) as:

[number of HAE attacks within first 3-months or second 3-months Treatment Period/ length of subject treatment in days] * 30.4375

with length of subjects treatment in days derived as:

- First 3-months Treatment Period: [the date of Study Visit Day 91 or the End of Study date [whatever is first] – the date of Study Visit Day 1 of the Treatment Period +1];

- Second 3-months Treatment Period: [the date of Study Visit Day 182 or the End of Study date [whatever is first] – the date of Study Visit Day 91 of the Treatment Period].

Technical Note: A subject who discontinued in the first three months of Treatment Period will have a time-normalized number of HAE attacks for the first 3-months but not for the second 3-months Treatment Period.

The percentage reduction in the time-normalized number of HAE attacks for the Active Arm compared to the time-normalized number of HAE attacks for the Placebo Arm (between subjects) will be calculated as:

$$100 * [(mean \text{ time-normalized number of HAE attacks for CSL312} - mean \text{ time-normalized number of HAE attacks for Placebo}) / mean \text{ time-normalized number of HAE attacks for Placebo}]$$

[figure not shown]
and

$$100 * [(median \text{ time-normalized number of HAE attacks for CSL312} - median \text{ time-normalized number of HAE attacks for Placebo}) / median \text{ time-normalized number of HAE attacks for Placebo}].$$

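### The primary estimand is labelled treatment policy, but attacks and follow-up beyond last dose + 30 days are dropped for subjects who stop drug and stay in the study

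*SAP*

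**What the plan says.** **SAP 10.1.1** adopts the treatment-policy strategy in the ITT population and states: "All observed values will be used regardless of occurrence of any of the following intercurrent events". Further on it adds an exception, which opens with "In case a subject discontinues study treatment due or not due to COVID-19 but continues participation in the study for more than 30 days" (counted from the final dose). For these subjects it says that "the HAE attacks until the last study drug administration plus 30 days will be included in the HAE attack analysis". The length of treatment for such a subject becomes the last dose date minus the Day 1 date, plus 31.

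**SAP 10.1** covers attacks that start after the first dose. Those "through Visit Day 182 (inclusive) or End of Study visit (whatever is first) will be counted for the Treatment Period and will be included"; the inclusion refers to the efficacy analyses, and the count is divided by the length of that same period. **SAP 8.3** introduces Table 8 as definitions that "will be used to define the durations used in the denominator of the time-normalized endpoints", and the table gives the same end date. Neither makes an exception for stopping drug.

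**Protocol 10.3.2.1** sets a treatment-policy estimand, lists early discontinuation as an intercurrent event, and follows subjects who stop drug to Day 182 or the Early Termination Visit. **Protocol 10.3.2.3** ends the denominator at the Day 182 visit or study discontinuation. **Protocol 4.3.1** encourages subjects who stop drug to stay until Day 182 so that assessments can be collected.

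**The concern.** A treatment-policy estimand uses outcomes after treatment stops. Cutting both the attack count and the time at last dose + 30 days replaces that strategy for treatment discontinuation, while the label stays the same.

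The intercurrent events are also listed inconsistently. SAP 7.1 says the primary estimand covers "early treatment or study discontinuation which might be caused by COVID-19", but the list in 10.1.1 names only study discontinuation. SAP Section 5 reports a COVID-19 update to the estimand and no other relevant change. It does not describe the cut-off, which applies whatever the reason for stopping.

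Two things are at stake. First, the primary result would be reported as a treatment-policy ITT effect although collected data were left out. Second, the SAP supports two derivations of the same endpoint. The primary analysis (10.1.2) follows 10.1.1, the within-subject percentage reduction (10.3.2.1) takes its rate from 10.1, and the 3-month analyses (10.3.2.4) state no cut-off.

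No planned analysis restores the dropped time. In the per-protocol analysis (10.1.3), "the HAE attacks until the last study drug administration plus 30 days thereafter will be included in the supplementary analysis of the primary estimand". The Poisson model uses the same length of treatment as its offset. The missing-data analysis covers only subjects who leave within 30 days of the first dose.

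**Working it through.** **1. The plan's own figure.** SAP 4.5 gives about 90% power for 24 + 16 subjects, Poisson means 0.3125 and 1.3 per month, two-sided 5%. The O'Brien-Castelloe approximation gives 0.907, and 4,000 simulated trials give 0.909. The stated power is reproduced, and the cut-off does not alter the sample size. At these rates the planned reduction in means is 1 - 0.3125/1.3 = 76.0%.

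**2. The two denominators.** With the last dose on day d, the SAP 10.1.1 length is d - 1 + 31 = d + 30 days. SAP 10.1, Table 8 and the protocol give 182 days for a subject who stays to Day 182.

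| Last dose | 10.1.1 length | Dropped | Share of 182 |
|---|---|---|---|
| Day 31 | 61 | 121 | 66% |
| Day 61 | 91 | 91 | 50% |
| Day 91 | 121 | 61 | 34% |
| Day 121 | 151 | 31 | 17% |

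A sixth dose on Day 151 would give 181 days, so completers are essentially untouched. Example for a last dose on Day 31, with 1 attack by Day 61 and 6 more by Day 182: 1/61 × 30.4375 = 0.50 per month under 10.1.1, and 7/182 × 30.4375 = 1.17 under 10.1.

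**3. Expected rate for one active subject who stops.** Assumptions that are not in the documents: 0.3125 per month up to the cut-off, and follow-up to Day 182. Two patterns after the cut-off were tried.

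- *Instant return to 1.3:* for d = 31, (0.3125 × 61 + 1.3 × 121)/182 = 0.969. For d = 91 the result is 0.643.
- *Gradual waning:* daily rate = 1.3 × [1 - C^h/(1.4^h + C^h)], with C = C0 × 2^(-t/19) at t days after the cut-off. The 19-day half-life is from protocol 1.2.3.1. The exposure-response points in protocol 3.3.2 (1.4, 3.3 and 7.8 µg/mL for 50, 75 and 90% reduction) give h = ln 9 / ln(7.8/1.4) = 1.28. For d = 31 the rate is 0.759 with C0 = 3.3 and 0.621 with C0 = 7.8. For d = 91 it is 0.456 and 0.355.

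**4. Reduction in means.** With k of 36 active subjects stopping and placebo at 1.3 throughout, active mean = ((36 - k) × 0.3125 + k × rate)/36. For k = 4, d = 31, instant return: (32 × 0.3125 + 4 × 0.969)/36 = 0.385, and 1 - 0.385/1.3 = 70.4%. With the cut-off it is 76.0% in every row.

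| k, last dose | Instant | Waning, C0 = 3.3 | Waning, C0 = 7.8 |
|---|---|---|---|
| 2, Day 31 | 73.2% | 74.1% | 74.6% |
| 4, Day 31 | 70.4% | 72.1% | 73.3% |
| 6, Day 31 | 67.5% | 70.2% | 72.0% |
| 4, Day 91 | 73.1% | 74.7% | 75.6% |

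**5. Medians and the test.** In 20,000 simulated Poisson trials (36 against 24, k = 4, d = 31), the average active median was 0.288 with the cut-off. With all data it was 0.324 (instant), 0.321 (C0 = 3.3) and 0.316 (C0 = 7.8). The placebo median was 1.273. The reduction in medians is therefore about 77.4% against 74.6% to 75.2%. The Wilcoxon test rejected in all of 2,000 simulated trials under either rule.

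**The case against.** The strongest reply is that 10.1.1 is a specific exception to a general definition. It has its own formula, and 10.1.2 explicitly follows 10.1.1, so a careful programmer would apply it. That is a natural reading for the primary test. It does not repair the label or the departure from the protocol, and it does not settle what 10.3.2.1 and 10.3.2.4 should do.

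Two lesser points concern wording. Section 5 does refer the reader to 10.1.1, and the variable is described as attacks during treatment. But Section 5 gives only COVID-19 as the reason, and both documents define treatment length by visit and end-of-study dates, not by dosing.

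The sizes can fairly be challenged. The number of subjects who stop is assumed, and four of 36 stopping after two doses and all staying is a demanding case. Instant loss of effect fits poorly with a 19-day half-life. Protocol 3.3.2 favours the higher starting concentration, although steady state may not hold after two doses. On that basis, with last dose on Day 31, one subject stopping gives 75.3% and two give 74.6%, against 76.0%. In the four-subject case the active median is identical under both rules in roughly 70% of simulated trials. All of this stands, and it limits the consequence without removing the inconsistency.

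It is also fair that an estimand may use different strategies for different events. Relabelling and declaring the rule would be a coherent alternative repair.

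**Conclusion.** The concern holds and should be fixed. Confidence is high that the passages contradict each other and low on the direction and size of any bias.

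The rule applies to both arms. If the effect wanes after stopping, dropping that time would probably favour CSL312. In the illustration with 4 of 36 stopping after Day 31, the gap is about 3 to 4 points in the reduction in means under gradual waning, 5.6 points as an upper bound, and 2 to 3 points in the reduction in medians. The bias is zero if no subject qualifies or the effect persists, and it could reverse if subjects who stop CSL312 improve on other therapy.

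The mean-based estimates are the most exposed. They include the percentage reduction behind H02 (SAP 4.2 and 10.3.2.4). The H01 decision is essentially unaffected at the planning rates.

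**What to change.** - In SAP 10.1.1, derive the primary endpoint from Day 1 to Visit Day 182 or End of Study, whichever is first, as in 10.1, Table 8 and the protocol. Include time and attacks after treatment discontinuation.
- Add treatment discontinuation to the intercurrent events listed there.
- Keep the last dose + 30 days version as a named while-on-treatment sensitivity analysis.
- Leave the rule for subjects observed less than 30 days, and its sensitivity analysis, unchanged.
- Limit to the per-protocol analysis the 10.1.1 provision that lets the blinded data review exclude data for missed doses.
- If the cut-off is kept for the primary analysis instead, relabel the strategy for treatment discontinuation, carry the rule through 10.1, Table 8, 10.3.2.1 and 10.3.2.4, and declare the departure in Section 5.

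A separate tidy-up, not needed for this point: Table 9 lists ITT as a possible exclusion for eligibility violations, which disagrees with the ITT definition in SAP 6.2.

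The cost is SAP wording and one extra programmed analysis, settled before unblinding. Collection of the data is already planned. The mean-based estimates may come out slightly less favourable.

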4.5 Determination of the Sample Size

In total, 60 subjects are planned to be randomized.

Forty subjects with C1-INH HAE type 1 and type 2 completing the 6-month Treatment Period are needed to achieve a power of approximately 90% for a two-sided Wilcoxon Test (alpha of 5%). Subjects will be randomized to the Active Arm or the Placebo Arm with a ratio of 3:2. An attack rate per month of 0.3125 for CSL312-treated subjects and of 1.3 for subjects receiving placebo are assumed. The monthly attack rates of placebo and of CSL312 are assumed to be Poisson distributed.

The sample size calculation is performed with SAS 9.4 using proc power procedure with twosamplewilcoxon test=WMW which performs power analyses for the Wilcoxon-Test for two independent groups, i.e. the CSL312 and the Placebo treatment in Study CSL312_3001. The Wilcoxon Rank Sum test is testing from departure from the null hypothesis and is assessing if there is a location shift between the distributions of the HAE attack rates of the CSL312 and the Placebo treatment. SAS Proc Power procedure uses the O'Brien-Castelloe approach to compute approximate power. Alpha is set to 5% [O'Brien & Castelloe, 2006]. The assumed monthly attack rates of placebo and of CSL312 (i.e. 1.3 and 0.3125 attacks/month, respectively) are used as the two means of the two Poisson distributions. The randomization ratio of 3:2 was implemented by GROUPNS = (24 16) resulting in a total sample size of 40 which is the lowest one reaching 90% power.

It is targeted to randomize approximately 5 adolescents into the treatment period with a randomization ratio of 3:2 (active:placebo).

To allow for sufficient safety data, to increase the likelihood of adolescents entering the study and, to have at least 40 subjects reaching the end of the study, an additional 20 subjects are planned to be randomized.

In case it is not feasible to randomize the targeted number of adolescents, the targeted total sample size will be achieved by randomizing the needed number with adult subjects.

In addition, it is targeted to include 5 Japanese subjects into the total 60 subjects randomized.

Based on Method 1 and Method 2 in the [Basic principles on Global Clinical Trials] the sample size of the Japanese subjects are planned as below. The point estimate of the endpoint in each arm for Japanese population and other regions (for Method 2) are assumed as the same as that for the global population.

Method 1

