Missing data is only given if subjects discontinue the study within 30 days after the first study drug administration in the treatment period. An approach to handle these missing data by sensitivity analysis is described in Section 10.1.2.

During the BDRM, it will be assessed if subjects have missed subsequent study drug administrations and if this might lead to the exclusion of subject's data from the analyses. All decisions will be documented in the BDRM minutes.

A COVID-19 diagnosis and resulting intercurrent events are irrelevant for the primary estimand. All observed values will be used regardless of occurrence of any of the following COVID-19 related intercurrent events: medications given to treat COVID-19 or COVID-19 vaccinations. Non-compliance to treatment and early discontinuation will be handled the same independent if it is related to COVID-19 or not.

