The mean time-normalized number of HAE attacks ratio for CSL312 relative to placebo and the corresponding 95% confidence interval estimated by the model described above will be used to calculate the percentage difference in the mean time-normalized number of HAE attacks for CSL312 from placebo as:

$$100\% * (\text{mean time-normalized number of HAE attacks ratio} - 1).$$

The 95% CI for the percentage difference will be calculated with the estimated upper and lower confidence limits for the mean time-normalized number of HAE attacks ratio, transform by subtracting 1 and multiplying by 100%.

The sensitivity analysis considering baseline attack rate will be carried out using the ITT Analysis Set.

Technical Note: the time-normalized baseline attack rate during Run-in Period (continuous) will be derived as defined in [Section 10.3.2.1](#).

Sensitivity Analysis for missing values

Missing values occur if the observation time for the treatment period is less than 30 days, i.e., a subject discontinued within 30 days after first study drug administration. Therefore, only a very low number of subjects with a missing primary endpoint are to be expected.

To assess the impact of missing data for the primary efficacy estimand a systematic approach will be applied. For each treatment arm, a range of values for the number of time-normalized HAE attacks per month from 0 to 6 subdivided into 9 increments between two consecutive integer values will be generated. All possible combinations from the subdivided ranges will be imputed to replace the missing values. For the comparison of active treatment versus placebo, observed and imputed data will be analyzed using the Wilcoxon Test and results will be classified into negative (i.e., placebo significantly better), neutral (i.e., no significant difference) and positive (i.e., active treatment significantly better).

A graph where the x-axis presents the subdivided range for placebo and the y-axis the subdivided range for the active treatment will visualize all scenarios and distinguished the different outcomes by different colors and symbols. The total number of subjects with missing outcome in placebo and active treatment arm will be added to the graph. This sensitivity analysis will only be applied to the ITT Analysis Set.

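### The missing-data sensitivity analysis covers only study exits within 30 days, so the constant-rate assumption made for every later leaver is never tested

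*SAP*

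**What the plan says.** **Estimand (SAP 10.1.1).** Treatment policy in all randomized subjects, for the monthly attack rate over Day 1 through Day 182. Early study discontinuation is listed among the intercurrent events that are to have no bearing. The population-level summary is the median.

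**Endpoint (SAP 10.1).** Attacks divided by days from Day 1 to the Day 182 visit or the End of Study date, whichever comes first, times 30.4375. It is not calculated when observation is shorter than 30 days.

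**Missing data.** SAP 10.1.1: "Missing data is only given if subjects discontinue the study within 30 days after the first study drug administration". For anyone who leaves later, it assumes a rate comparable to that of subjects observed for six months: "This assumption is based on CSL312_2001 data which showed that the CSL312 treatment effect was maintained over time". SAP 8.1 states the same assumption and adds that phase 2 showed no pattern in attacks under either treatment.

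**Sensitivity analysis (SAP 10.1.2).** "Missing values occur if the observation time for the treatment period is less than 30 days". Only those cases are imputed, over a grid of 0 to 6 attacks per month in each arm, and only the Wilcoxon result is reported.

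**Treatment stoppers who stay in the study (SAP 10.1.1).** If they remain more than 30 days beyond the last dose, attacks and days count only to last dose plus 30 days.

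**Where the size of effect is reported.** The percentage reduction in means is confirmatory hypothesis H02 (SAP 4.2 and 10.3.2.4). The Poisson model in SAP 10.1.2 gives a percentage difference.

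**The concern.** A treatment-policy estimand over 182 days asks for attacks on all 182 days. For a subject who leaves on Day 60, 182 − 60 = 122 days are unobserved. Dividing by observed time makes the endpoint calculable, but it does so by assuming that the earlier rate continues. That is an imputation and should be tested as one.

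The support offered does not reach the gap. A maintained effect in phase 2 concerns subjects under treatment, and the double-blind part lasted 13 weeks (Protocol 1.2.3.2). It says nothing about attacks after a subject has left.

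No other planned analysis fills the gap. The Poisson model's log-time offset builds in the same constant rate. The per-protocol analysis uses the same observed-time variable. The second three-month analysis has no value for subjects who left in the first three months. The cut at last dose plus 30 days also discards observed off-drug attacks that could have informed the question.

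At stake is the size of the reported reduction in H02 and in the Poisson model.

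**Working it through.** **Inputs from the documents.** SAP 4.5: "An attack rate per month of 0.3125 for CSL312-treated subjects and of 1.3 for subjects receiving placebo are assumed"; "The randomization ratio of 3:2 was implemented by GROUPNS = (24 16) resulting in a total sample size of 40"; "In total, 60 subjects are planned to be randomized", split 36 CSL312 and 24 placebo. Follow-up is 182 days. The half-life is about 19 days (Protocol 1.2.3.1).

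**Assumptions, not in the documents.** The share d of the CSL312 arm that leaves after Day 30; exit day uniform over Days 31 to 181; the rate after exit; placebo leavers staying at 1.3. SAP 4.5 gives no dropout rate. It says that "an additional 20 subjects are planned to be randomized", partly for safety data and adolescent recruitment, so 20/60 = 33% is a ceiling.

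**Step 1: the plan's own figures.** The O'Brien-Castelloe method named in the SAP gives 90.7% power for 24 + 16, and simulation gives about 92%. The stated figure of about 90% is reproduced. The implied reduction is 1 − 0.3125/1.3 = 76.0%.

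**Step 2: one exit day.** The plan carries 0.3125 forward. If a fraction f of the gap to placebo returns after exit on day t:

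overstatement = d × (182 − t)/182 × f × (1.3 − 0.3125)/1.3, where the last ratio is 0.7596.

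For d = 10%, t = 91, f = 1: 0.10 × 0.5 × 0.7596 = 3.8 points. For d = 5% and an early exit at t = 45: 0.05 × 137/182 × 0.7596 = 2.9 points. With f = 0 it is zero.

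**Step 3: exits spread over Days 31 to 181.** The mean number of unobserved days is 76.
- Immediate full return, 4 of 36 leaving: 4/36 × 76/182 × 0.7596 = 3.5 points.
- A 30-day lag before the rate rises leaves on average 7,381/151 = 48.9 days at the higher rate: 4/36 × 48.9/182 × 0.7596 = 2.3 points (2.2 in simulation).

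Simulated overstatement in percentage points, full return, 36 versus 24 subjects:

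| CSL312 leavers | Mean, 30-day lag | Mean, immediate | Median, 30-day lag | Median, immediate |
|---|---|---|---|---|
| 2 of 36 (6%) | 1.1 | 1.8 | 0.8 | 1.1 |
| 4 of 36 (11%) | 2.2 | 3.5 | 1.5 | 2.0 |
| 7 of 36 (19%) | 4.0 | 6.1 | 2.7 | 3.5 |
| 12 of 36 (33%) | 6.8 | 10.5 | 4.8 | 6.6 |

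If only half the gap returns at once, the mean figures are 0.9, 1.8, 3.1 and 5.3.

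**Step 4: plausibility of the lag.** Protocol 3.3.2 links 90% and 50% attack reduction to 7.8 and 1.4 µg/mL. At a 19-day half-life that fall takes 19 × log2(7.8/1.4) = 47 days. A Hill curve through the protocol's three concentrations, with this decay, gives 1.7 to 1.8 points at 10% leaving and 3.4 to 3.7 at 20%. Gradual loss therefore sits near the lagged figures, and immediate return is an upper bound.

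**Step 5: the primary test.** Over 182/30.4375 = 5.98 months at the SAP's Poisson rates, the Wilcoxon test rejected in essentially 100% of simulated trials, both before and after the change.

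**The case against.** The assumption is disclosed, not hidden. SAP 8.1 and 10.1.1 state it and tie it to phase 2 data that are not available here. Heavy exit is also discouraged: treatment stoppers are encouraged to remain to Day 182 (Protocol 4.3.1 and 4.3.2), and only those who complete may roll over to the open-label study (Protocol 3.1.4). All of this stands, and it limits the likely size. It does not replace a test of the assumption.

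Three stronger readings are tempting, and the documents support none of them.
- A reader might infer that the primary result is at risk. Under the SAP's rates it is not.
- A reader might infer that the bias always favours CSL312. It does so only if leavers' attacks rise after exit. A subject who leaves because of poor response already carries a high rate forward and adds little or no bias.
- A reader might take the one-third row as an expectation. The extra 20 subjects serve several purposes, so it is a ceiling.

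The median, which is the estimand's own summary, also moves less than the mean.

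**Conclusion.** The concern holds as a gap in the sensitivity analysis. The plan declares a treatment-policy estimand to Day 182, assumes a constant rate for everyone who leaves after Day 30, and tests missing data only for earlier exits.

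The exposure is in the mean-based percentage reduction (H02 and the Poisson model). It is about 2 to 4 points with about 10% of the CSL312 arm leaving and 4 to 6 points with about 20%, for a return to the placebo rate after a 30-day lag or at once. At 5% leaving it is about 2 points or less, though early exits with full return can reach 2.9. It is zero if leavers keep their on-study rate. These figures rest on the SAP's attack rates and on assumed dropout, exit timing and post-exit rates.

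The SAP should be changed, but the point does not put the primary conclusion in doubt.

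**What to change.** 1. Delete the statement in SAP 10.1.1 that confines missing data to exits within 30 days, and align SAP 8.1 and 10.1.2 with it.
2. Extend the 0-to-6 grid in SAP 10.1.2 to every subject who discontinues the study before the Day 182 visit. Keep observed attacks, impute only the days from exit to Day 182 at each grid rate by arm, and recompute the rate.
3. Trigger this by study discontinuation, not by day count. The Day 182 visit has a ±4-day window. An attack-free completer seen on Day 178 would otherwise have 4 days imputed, which at 6 per month adds 6 × 4/182 = 0.13 per month. That is close to the 30.4375/182 = 0.17 of one real attack, and it would break ties at zero.
4. Report the Wilcoxon result and both the mean and the median percentage reduction. Name one reference scenario: CSL312 leavers at the observed placebo-arm rate after exit.
5. In the same analysis, use all attacks observed to Day 182 for subjects who stop treatment but stay in the study, without the cut at last dose plus 30 days.

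The cost is SAP wording, a small extension of an already planned program, and a sensitivity estimate that may be less favourable to CSL312.
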